#### **Causal relationship of adverse events with the targeted oral therapy**

Medical judgment should be used to determine the relationship with the oral targeted therapy while considering all relevant factors, including pattern of reaction, temporal relationship, de-challenge or re-challenge, confounding factors such as concomitant medication, concomitant diseases and relevant history.

#### **Worsening of the underlying disease or other pre-existing conditions**

Worsening of the underlying disease or other pre-existing conditions and changes in vital signs, ECG, physical examination, and laboratory test results will be recorded as an AE in the CRF, if they are judged clinically relevant by the investigator.

#### **Other pharmacovigilance information**

- Non-conform use of the product i.e. any use outside the marketing authorisation (for instance: overdose, medical error, intentional misuse or abuse, administration outside the marketing authorisation, not in conformity with the marketing authorisation, administrated for a condition not cover by the marketing authorisation),
- Product's exposure during pregnancy or breast-feeding,
- Product's exposure during conception (father),
- Suspicion of contamination with an infectious agent,
- Suspicion of AE related to a professional exposure,
- Lack of efficacy or any increased in therapeutic effect or any unexpected benefit
- Any interaction with other product (drugs, food, tobacco, alcohol, radiation).

### 5.3.2.2 Adverse event and reporting

All SAEs, non-serious AEs and others PV information, occurring during the course of the study (i.e., from signing the informed consent onwards through D90) will be collected, documented and reported to the sponsor or the CRO in charge of the data monitoring by the investigator on the appropriate reporting forms (AE page of the CRF or SAE form).

For each adverse event, the investigator will provide the onset date, end date, intensity, treatment required, outcome, seriousness, causal relationship, and action taken with the targeted oral therapy. The investigator will determine the relationship of the oral targeted therapy to all AEs.

All personnel involved in the study (investigator, the Patientys call centre nurse, general practitioner, centre personnel...) must immediately report any SAE that they encounter to the CRO responsible of the data monitoring. The event must be notified within 24h, via telephone or FAX using the SAE reporting form to:

**Follow-up of SAEs - PARTAGE**

Fax: [REDACTED]

Back-up fax: [REDACTED]

E-mail: [REDACTED]

The notification of the SAEs must be immediate whether the oral targeted therapy was administered or not, whether there is a causal relationship or not, or whether the information is initial information or additional information.

All other non-serious AEs and PV information must be reported to the CRO in charge of the study management within 7 calendar days of knowledge. The CRO must inform Boehringer Ingelheim within 7 calendar days of notification by the investigator.

#### Pregnancy

Any pregnancy occurring during the course of this study must be immediately reported following the same SAE reporting procedure using the pregnancy form. The pregnancy must be followed-up, its outcome documented, and the pregnancy form should be completed. In the absence of any AE, only the pregnancy monitoring is to be completed.

Health professional should comply with the applicable legislation regarding reporting obligations (Article R5121-161 of the French public health code).

### 5.3.3 Assessment of other safety parameters

Not applicable

#### **5.4 APPROPRIATENESS OF MEASUREMENTS**

All clinical evaluations made in this study are part of the routine monitoring of patients with NSCLC. The questionnaires used during patients follow-up are validated questionnaires, with the exception of the satisfaction questionnaires.

## 6. INVESTIGATIONAL PLAN

### 6.1 VISIT SCHEDULE

**Table 2 Visit schedule and data collection**

|   | D0      | D1a | D7a | D14a | D21a | D28a | D30
M1 | D45a | D59a | D60
M2 | DJ89a | D90b
M3 |
|---|----------------|-----------------------|-----------------------|------------------------|------------------------|------------------------|-------------------|------------------------|------------------------|-------------------|-------------------------|-------------------------------|
|   | MV Incl | NFPC 1                | NFPC 2                | NFPC 3                 | NFPC 4                 | NFPC 5                 | MV1        | NFPC 6                 | NFPC 7                 | MV2        | NFPC 8                  | MV3                    |
| Written consent   | X              |                       |                       |                        |                        |                        |                   |                        |                        |                   |                         |                               |
| Verification of eligibility   | X              |                       |                       |                        |                        |                        |                   |                        |                        |                   |                         |                               |
| Documentation of patient's acceptance or rejection of participation in the study file | X              |                       |                       |                        |                        |                        |                   |                        |                        |                   |                         |                               |
| Demographic information c  | X              |                       |                       |                        |                        |                        |                   |                        |                        |                   |                         |                               |
| Physical exam d  | X              |                       |                       |                        |                        |                        |                   |                        |                        |                   |                         |                               |
| NSCLC characteristics e  | X              |                       |                       |                        |                        |                        |                   |                        |                        |                   |                         |                               |
| Past medical history, past treatments   | X              |                       |                       |                        |                        |                        |                   |                        |                        |                   |                         |                               |
| Concomitant diseases, concomitant medications   | X              |                       |                       |                        |                        |                        | X                 |                        |                        | X                 |                         | X                             |
| Randomisation   | X              |                       |                       |                        |                        |                        |                   |                        |                        |                   |                         |                               |
| Patient diary delivery  | X              |                       |                       |                        |                        |                        |                   |                        |                        |                   |                         |                               |
| Clinical evaluation by Patientys nurse  |                | X                     | X                     | X                      | X                      | X                      |                   | X                      | X                      |                   | X                       |                               |
| Collection of AEs   | X              | X                     | X                     | X                      | X                      | X                      | X                 | X                      | X                      | X                 | X                       | X                             |
| Patient compliance (returned tablets and Girerd questionnaire)                        |                |                       |                       |                        |                        |                        | X                 |                        |                        | X                 |                         | X                             |
| Patient quality of life questionnaire   | X              |                       |                       |                        |                        |                        | X                 |                        |                        |                   |                         | X                             |
| Patient global satisfaction questionnaires  |                |                       |                       |                        |                        |                        |                   |                        |                        |                   |                         | X                             |
| Data collection on use of healthcare services   |                |                       |                       |                        |                        |                        | X                 |                        |                        | X                 |                         | X                             |
| General practitioner and/or pharmacist global satisfaction questionnaires             |                |                       |                       |                        |                        |                        |                   |                        |                        |                   |                         | X                             |
| Investigator global satisfaction questionnaires                                       |                |                       |                       |                        |                        |                        |                   |                        |                        |                   |                         | X                             |

a Only for patients 'With nurse-led follow-up' group

b Or end of study visit if the patient withdraws prematurely from the study

c Including age, gender, weight, height

d Complete physical exam at inclusion visit including: Vital signs (Heart & respiratory rate, blood pressure, temperature), and collection of the cutaneous, gastro-intestinal, respiratory, eye, cardiovascular and allergic symptoms

e Diagnosis date, disease stage, performance status (ECOG), biopsy date, type of mutation(s), method of mutation typing, previous treatments of NSCLC

f The drug accountability of taken and not taken tablets will be made by the medical team in the Case Report Form

D = day ; M = month ; MV = medical visit according to the routine practice of the centre, NFPC= nurse follow-up phone call, Incl.= inclusion, NSCLC = non-small-cell lung cancer ;

AE= adverse event.

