### **3.3.4      Removal of patients from therapy or assessments**

Patients can decide to discontinue their participation in this study at any time.

Boehringer Ingelheim reserves the right to discontinue the overall study or in a particular centre for the following reasons:

- Inability to recruit the planned number of subjects across centres or in a particular centre.
- Evidence of information that could significantly affect the continuation of the study, or for other administrative reasons.
- Violation of Good Clinical Practice (GCP) or contract, by a study centre or an investigator, preventing the proper conduct of the study.

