## **5.2 SECONDARY ENDPOINTS**

### **5.2.1 Secondary endpoints**

The following secondary endpoints will be evaluated in the study:

- Score (0–6) obtained with the Girerd questionnaire at D30, D60 and D90.
- Cumulated dose of oral targeted therapy not taken (all categories) following decision of the medical team.
- Cumulated dose of oral targeted therapy not taken due to dose reduction following decision of the medical team.

- Cumulated dose of oral targeted therapy not taken due to temporary or definitive interruption following the medical team decision.
- Cumulated dose of oral targeted therapy not taken (all categories) following patient decision.
- Cumulated dose of oral targeted therapy not taken due to dose reduction following patient decision.
- Cumulated dose of oral targeted therapy not taken due to temporary or definitive interruption following patient decision.
- VAS score (0–10) for overall patient satisfaction with the level of care (information, advice) at D90.
- Absolute variation observed for the quality of life questionnaire FACT Lung score between D30 and D0, between D90 and D30 and between D90 and D0.
- Number of emergency admissions (related to the treatment) during the 3-month follow-up.
- Number and duration of unplanned hospitalizations (related to the treatment) during the 3-month follow-up.
- Number of unplanned visits to the investigator during the 3-month follow-up.
- Number of unplanned visits to a specialist, whatever is his specialty, other than the investigator during the 3-month follow-up.
- Number of unplanned visits to the general practitioner during the 3-month follow-up.
- VAS score (0–10) for overall investigator satisfaction with the level of patient care at D90.
- VAS score (0–10) for overall general practitioner satisfaction with the level of patient care at D90 (only for the patients with 'remote additional personalised nurse-led follow-up')
- VAS score (0–10) for overall pharmacist satisfaction with the level of patient care at D90 (only for the patients with 'remote additional personalised nurse-led follow-up').
- Number of calls made by the patients to their general practitioner during the 3-month follow-up.
- Number of calls made by the general practitioner to the patient during the 3-month follow-up.
- Number of calls made by the patients to their medical team during the 3-month follow-up.
- Number of calls made by the medical team to their patient during the 3-month follow-up.

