## **6.2 DETAILS OF DATA COLLECTION AT EACH VISIT/ PHONE CALL**

### **6.2.1 Inclusion (Incl. MV)**

During the inclusion consultation, the medical team will ask the patient to participate in this study. Written consent will be obtained; however if the patient refuses to participate in the study, the refusal with the corresponding reason, if available, will be documented in the study registry. The patient accepting to participate in the study will be randomised to receive or not a remote additional nurse-led follow-up during the follow-up period (randomisation ratio of 3:1).

The registration form must be completed and forwarded to Patientys by e-mail or FAX.

If the patient agrees to participate in the study, the investigator will collect the following data:

- Demographic information (age, gender, weight, height).
- NSCLC characteristics (date of first diagnosis, disease stage, performance status from the Eastern Cooperative Oncology Group [ECOG], biopsy date, type of mutation(s) detected, test/method used to assess mutation and previous treatments).
- Medical history, concomitant diseases, previous and concomitant treatment.
- Results of the complete physical examination: vital signs (heart and respiratory rate, blood pressure, temperature), and presence of any of the following symptoms: coetaneous, gastrointestinal, respiratory, ocular, cardiovascular and allergic.

As with any initiation of oral targeted therapy treatment, the medical team will counsel the patient on the oral targeted therapy, treatment schedule and precautions (lifestyle changes) to be taken in order to prevent treatment related adverse events, in addition to giving the patient a diary to report information related to the utilisation of healthcare services (telephone calls with or visits to their general practitioner or specialist, with any specialty).

During this consultation, and as per routine practice, the medical team will set the schedule of upcoming consultations. In this study, 3 data collection time-points at monthly intervals are defined (D30, D60, and D90). The frequency of visits should not be adjusted and the medical team should maintain his routine practice (example: if the investigator is used to see the patient on D15, the visit will still take place, but no information, except pharmacovigilance data, will be collected). As such, the data from the closest defined visit will be reported in the CRF.

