### **6.2.2 Other visits (MV1, MV2, MV3)**

At the 2nd and 3rd consultation visits (D30 and D60) during which data will be collected, the patient will be asked to:

- Complete the compliance questionnaire (Girerd).
- Complete the quality of life questionnaire (FACT Lung; only on D30).
- Bring their oral targeted therapy packets (empty or started) prescribed/consumed since the previous consultation visit.

- Bring their patient diary.

All the questionnaires will be completed before the start of consultations, in the doctor's office or any other available private place.

The medical team will record the number of tablets taken and not taken, and will report this information in the patient's CRF.

Adverse events and concomitant diseases and medications will be collected during these consultations. Data on the utilization of healthcare services (hospitalizations, emergency room visits, unscheduled consultation visits), including the number of visits and the number of calls to the general practitioner, will also be collected using the information reported by the patient in their patient diary.

During the last consultation visit (MV3 on D90), the patient will be asked to:

- Complete the compliance questionnaire (Girerd),
- Complete the quality of life questionnaire (FACT Lung),
- Complete the global satisfaction questionnaire,
- Bring their oral targeted therapy packets (empty or started) prescribed/consumed since the previous consultation visit,
- Bring their patient diary.

All the questionnaires will be completed before the start of consultations, in the doctor's office or any other available private place.

The medical team will record the number of tablets taken and not taken, and will report this information in the patient's CRF.

Adverse events and concomitant diseases and medications will be collected during these consultations. Data on the utilization of healthcare services will also be collected using the information reported by the patient in their patient diary.

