### **7.3.3 Secondary analyses**

In addition to the primary analysis, a secondary analysis of Girerd questionnaire scores will be performed.

This questionnaire is composed of 6 binary questions (yes/no) and is used to assess treatment compliance. The final score obtained is the number of questions to which the patient responded 'yes'. Thus, the score ranges from 0 to 6.

A patient will be classified as:

- Good compliant: score = 0.
- Minor non-compliant: score = 1 or 2.
- Non-compliant: score > 2.

A sub-group descriptive analysis of patients per score category on D30, D60 and D90 will be presented: number of observed values, percentage, and 2-sided 95% confidence interval.

In addition, the percentage of patients with good compliance (score = 0) to the percentage of patients with minor non-compliance and / or non-compliance (score > 0) will be compared at each time point (D30, D60, D90), between the 2 groups of patients ('With nurse-led follow-up' and 'Without nurse-led follow-up'), using Chi-2 or Fisher-exact test.

The cumulated doses (mg) of the oral targeted therapy not taken during the 3-month follow-up by decision of the medical team (with details by type: dose reduction, temporary or definitive discontinuation) / by decision of the patient him/herself (with details by type: dose reduction, temporary or definitive discontinuation) will be described for each follow-up group, using number of observed values, mean, standard deviation, median, lower quartile, upper quartile, minimum, maximum, 2-sided 95% confidence interval of the mean.

Analysis of other secondary endpoints will simply be descriptive and inferential as described in the general statistical considerations, namely:

- Quantitative variables:
  - VAS score (0–10) for overall patient satisfaction with the level of self-care (information, counselling, advice...) at D90.
  - Absolute variation observed for the quality of life questionnaire FACT Lung score between D30 and D0, between D90 and D0, and between D30 and D90.
  - Duration of unplanned hospitalisations during the 3-month follow-up.
  - VAS score (0–10) for overall investigator satisfaction with the level of patient self-care at D90.
  - VAS score (0–10) for overall general practitioner satisfaction with the level of patient self-care at D90 (only for the patients with 'remote additional personalised nurse-led follow-up').

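### Early end-of-study visits are filed under D90, and no rule separates their questionnaires from true D90 assessments

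*Combined protocol and SAP*

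**What the plan says.** **Where an early exit is placed.** Table 1 (Flow Chart) and Table 2 (Section 6.1) attach footnote b to the D90/M3/MV3 column: "Or end of study visit if the patient withdraws prematurely from the study". The column marks the tablet count with Girerd, the quality-of-life form and patient satisfaction. No other column exists for an early exit. Section 3.3.4 sets no limit on timing: "Patients can decide to discontinue their participation in this study at any time". Section 6.2.2 lists the final questionnaires under one occasion only: "During the last consultation visit (MV3 on D90), the patient will be asked to".

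**How visits are matched to time points.** Sections 3.1 and 6.2.1 fix data collection at D30, D60 and D90 around routine visits, and say that "the data from the closest defined visit will be reported in the CRF". No day limits are given, and withdrawal visits are not mentioned.

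**How the forms are analysed.**
- Girerd good compliance (Section 7.3.3): "will be compared at each time point (D30, D60, D90), between the 2 groups of patients", by Chi-2 or Fisher test.
- FACT-Lung (Section 7.3.3): changes in "FACT Lung score between D30 and D0, between D90 and D0, and between D30 and D90".
- Satisfaction VAS (Section 5.2.1): "overall patient satisfaction with the level of care (information, advice) at D90".
- Repeated measures (Section 7.3.3): a mixed model with a follow-up by visit interaction.

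Section 7.4 foresees no general missing-data method and uses all available data. The sensitivity analysis that it defers to the SAP concerns the primary endpoint only.

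**The concern.** The only text that places an early withdrawer's last visit puts it in the D90 column, and the analyses are keyed to that nominal label. If the label is carried into the dataset, a D90 value that is really missing becomes an observed one. In effect the last score is carried forward, although Section 7.4 says no method of that kind is foreseen.

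Three sets of results are exposed: the D90 comparisons of Girerd and satisfaction, the FACT-Lung changes that end at D90, and the visit interaction in the mixed model. The study is open-label, and the calls are meant to reassure patients and help with adverse events. The share or timing of exits could therefore differ between arms. If it did, the D90 comparison would partly compare different times since start of treatment.

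**Working it through.** There is no figure in the plan to reproduce; the question is one of visit labelling.

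**Step 1: the two placement rules for one visit.** Take exits at D20 and D35. Both days are chosen only for illustration.

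| Exit day | Days from D30 | Days from D60 | Days from D90 | Nearest time point | Footnote b column |
|---|---|---|---|---|---|
| D20 | 10 | 40 | 70 | D30 | D90 |
| D35 | 5 | 25 | 55 | D30 | D90 |

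The closest-visit idea and the footnote disagree in both cases, and no text says which prevails.

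**Step 2: what the footnote does to the change scores.**
- Exit at D20, before any D30 visit: the nominal D90–D0 change covers 20 days instead of 90. The D90–D30 change cannot be formed.
- Exit at D35, after a D30 visit: the nominal D90–D30 change covers 35 − 30 = 5 days instead of 60. The D90–D0 change covers 35 days.

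**Step 3: how far the label could drift.** No withdrawal rate is stated, so the share *w* leaving with a completed exit visit is an assumption. It is applied to the planned 100 and 300 patients, with all others seen exactly at D90. Mean actual day of nominal D90 data = (1 − w) × 90 + w × exit day.

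| w (assumed) | Early records, without / with calls | Mean day if exits at D20 | Mean day if exits at D45 |
|---|---|---|---|
| 5% | 5 / 15 | 86.5 | 87.75 |
| 10% | 10 / 30 | 83 | 85.5 |
| 20% | 20 / 60 | 76 | 81 |

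For example, 0.90 × 90 + 0.10 × 20 = 83. If one arm had 20% and the other 10%, all at D20, the arms would differ by 83 − 76 = 7 days in mean assessment day. With 10% against 5% the difference would be 86.5 − 83 = 3.5 days. Nothing in the documents indicates which arm would have more exits.

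**Step 4: from days to scores.** A bias in a D90 score would need, in addition, the gap between exit scores and the scores those patients would have had at D90. The documents give no such gap, so the calculation stops here.

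**The case against.** The case on the other side is substantial.

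1. *The footnote governs data collection.* It stands under a visit schedule, and no sentence in Sections 5.2, 7.3.3 or 7.4 says an early form counts as D90. This stands. A reader might infer that the plan directs early forms to be analysed as D90 results, but the documents do not say so. The CRF is not among the documents either, so it may capture the true date.
2. *The closest-visit wording would send D20 or D35 to D30.* It points that way, but it concerns routine visits, has no day limits and does not mention withdrawal. It leaves two texts unreconciled.
3. *The analysis population may remove leavers.* Section 7.3 requires information on the major criteria, the primary one in particular. Some early withdrawers may drop out on that ground. However, the primary criterion is a sum of tablets counted between visits, and Section 7.3 does not say whether a patient with partial counts qualifies.
4. *Leavers need not be patients with toxicity or dissatisfaction.* A reader might infer this, but the documents do not support it. Footnote b concerns leaving the study; definitive interruption of treatment is counted as dose not taken within follow-up. No reasons for withdrawal are given.
5. *The 20% in Section 7.6 might be read as the share affected.* It is the share non-evaluable for the primary criterion, not an early-exit rate.
6. *Visit windows normally belong in the SAP.* That is so, and Section 8.3.1 requires it to be final before database lock. But the SAP deferral in Section 7.4 covers only missing primary data, so nothing yet commits the SAP to a rule for these questionnaires.

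**Conclusion.** The point holds as a conflict and a gap. Footnote b is the only text that places an early end-of-study visit, it places it at D90, and nothing in Sections 5.2, 7.3.3 or 7.4 separates it from a true D90 visit. Followed literally, early-exit Girerd, FACT-Lung and satisfaction scores enter the D90 comparisons, the changes ending at D90 and the follow-up by visit model. Two programmers could build different D90 datasets from the same text.

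The size and direction of any bias cannot be computed. The drift in mean assessment day shown above rests wholly on assumed withdrawal shares and exit days, and a bias in score points would need further assumptions. Only secondary endpoints are affected; the primary test and the sample size are untouched. The correction is cheap and can be made before any result is seen, so it should be made.

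**What to change.** - **Recording.** Keep the early end-of-study visit, but give it its own column and CRF page with the actual date, and remove footnote b from D90. Keep its tablet count in the cumulated dose, so that no primary-endpoint data are lost.
- **Assignment.** In the SAP, assign Girerd and FACT-Lung by actual day, using stated windows around each time point scheduled for that instrument. A form counts as D90 only inside the D90 window; otherwise D90 is missing. Nearest-point assignment without a bound is not enough. FACT-Lung is not collected at D60, so an exit form at D62 is 28 days from D90 and 32 from D30, and would still be labelled D90.
- **Analysis.** Use the repeated-measures model already planned in Section 7.3.3 for the repeated questionnaires. Add a sensitivity analysis with exit values included at D90. The simple D90 tests (Chi-2/Fisher, Student/Wilcoxon) drop patients with no D90 value, and that can itself be selective.
- **Satisfaction.** Report the VAS at early exit separately from the D90 VAS.

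The cost is a changed footnote, one CRF page and a short SAP paragraph. The downside is fewer D90 values in the simple between-group tests. The model also relies on missingness being explained by the observed data, which is why the sensitivity analysis is needed.
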